10.3.4. Nonpharmacogenetic Biomarker Evaluation and Patient Tailoring

10.3.4.1. Sample Requirements and Preparation

Collection of samples for biomarker research is required for this study. Refer to the Study Schedule ([Attachment 1](#)) for timing of sample collection.

The research on stored samples from this study may look at the proteins or other biochemical markers to learn more about compound-specific disease states or how patients respond to or tolerate treatment with LY2157299 or other compounds/medications administered during this study. Stored samples may also be used in validating diagnostic tools or assay(s) related to patient tailoring and disease state.

At baseline, before the patient receives study drug, the following samples will be collected:

- pretreatment formalin-fixed paraffin-embedded (FFPE) tumor tissue taken from the original diagnostic tumor specimen if available (paraffin blocks or approximately 10 unstained slides cut from that block, for correlation studies of molecular markers)
- optional tumor biopsy
- plasma

At Cycle 1, the following samples will be collected:

- plasma

At Cycle 2, an optional tumor biopsy will be collected.

After Cycle 2, at the time of disease progression and only if the patient is on study therapy, the following samples will be collected:

- plasma

10.3.4.2. Sample Labeling

All samples will be labeled with the same identification code assigned to the patient. This code will be used in lieu of the patient's name to protect the patient's identity.

Blood, serum, and plasma samples must be collected and shipped according to instructions provided in the central laboratory manual.

10.3.4.3. Sample Shipping and Handling

Samples will be shipped by the local laboratory to the designated research laboratories, according to the instructions in the central laboratory manual. Designated research laboratories are associated with Lilly and are located in the US and EU.

10.4. Appropriateness of Measurements

There are no surrogate endpoints used in this study. All efficacy and safety assessments used in this study are standard and appropriate for an oncology study.

11. Data Quality Assurance

To ensure accurate, complete, and reliable data, Lilly or its representatives will do the following:

- provide instructional material to the study sites, as appropriate
- sponsor a start-up training session to instruct the investigators and study coordinators. This session will give instruction on the protocol, the completion of the CRFs, and study procedures.
- make periodic visits to the study site
- be available for consultation and stay in contact with the study-site personnel by mail, telephone, and/or fax
- review and evaluate CRF data and use standard computer edits to detect errors in data collection
- conduct a quality review of the database

In addition, Lilly or its representatives may periodically check a sample of the patient data recorded against source documents at the study site. The study may be audited by Lilly or its representatives and/or regulatory agencies at any time. Investigators will be given notice before an audit occurs.

To ensure the safety of participants in the study, and to ensure accurate, complete, and reliable data, the investigator will keep records of laboratory tests, clinical notes, and patient medical records in the patient files as original source documents for the study. If requested, the investigator will provide the sponsor, applicable regulatory agencies, and applicable ERBs with direct access to original source documents.

12.1. Determination of Sample Size

This section describes how amendments to the protocol have affected the determination in sample size.

The original protocol and Amendment (a) planned to enroll 140 Child-Pugh Class A or B7 patients with HCC in this study. Each patient was randomized into 1 of 2 cohorts to receive either 160 or 300 mg/day of LY2157299. Both cohorts were proportionately balanced for 3 factors: baseline AFP levels (≤ 400 ng/mL, >400 ng/mL), etiology (alcohol, viral, other), and sorafenib-naive or not.

This sample size meant that if the study had completed to its maximum enrollment, there would be approximately 80% power to detect a HR of 1.5 as statistically significant at the 20% level (2-sided) between the 2 doses. This was assuming an exponential survival distribution, a 24-month accrual period, 6-month observation period after the last patient enrolled, and no loss to follow-up, and anticipation of around 129 events being observed.

There were 2 planned interim analyses. The first interim analysis assessed safety after 10 patients enrolled in each dose cohort (20 total patients) and completed 1 cycle of treatment and assessed PK when 10 patients/dose were eligible for PK assessments (all samples including the Day 15 sample). After the first interim analysis, it was decided that enrollment into both doses should continue. The second interim analysis was planned after 40 patients had enrolled into each dose cohort (80 total patients) and actively followed for 3 months or until progressive disease or death had been observed to further investigate safety and to compare the progressive disease efficacy measures between the 2 dose cohorts.

Consideration was also to be given to the number of patients who were free from progression at 3 months at the second interim analysis. Given that some of the patients included in this study may have previously progressed on sorafenib, a median TTP of 4.5 months would have been

considered promising, representing a 60% improvement over best supportive care of these patients (median TTP of 3 months). If the true median TTP in any dose group is 4.5 months or 3 months, then 63% or 50%, respectively, are expected to be free from disease progression at 3 months.

Details of the decision criteria for each of the planned interim analyses are provided in Section [12.2.14](#).

The first interim analysis was completed. However, an additional data review was carried out prior to the planned second interim analysis, and this was when 64 patients had received at least 1 dose of study drug and were reported in the clinical database. Of these, 44 patients had completed at least 3 cycles of treatment or discontinued from study treatment. The decision from this review was to stop enrollment into Cohort 1 (at 37 patients) and to complete enrollment of Cohort 2 (n=70 patients). In addition, the protocol was amended (Amendment [b]) to have 2, and possibly 3, parts in this study. The 2 cohorts planned in the original protocol and in the Amendment (a) were designated as Part A. Part B was to enroll 40 Child-Pugh Class A or B7 patients with HCC with AFP levels <1.5x ULN. Part C was to enroll approximately 40 Child-Pugh B7 or B8 status patients.

Therefore, the study (Amendment [b]) planned to enroll a total of 147 patients, and possibly 187 patients: 107 in Part A (37 in Cohort 1, 70 in Cohort 2), 40 in Part B, and 40 in Part C (if implemented). Given these changes, the primary objective of the study is now restricted to characterize both the TTP distributions and the effect on TGF- β -associated serum biomarkers (for example, TGF- β , AFP, E-cadherin) of the 2 doses of LY2157299 in patients with HCC with elevated AFP levels and in patients with normal AFP levels dosed at 300 mg/day, and not to carry out any formal comparisons. Rather, estimates of treatment differences between the 2 doses in Part A, and between Part A 300 mg/day and Part B and Part C patients would be provided.

Two interim analyses were planned for Amendment (b) – one after the 70 patients with elevated AFP levels had enrolled into Cohort 2 and started Cycle 1, and the second after 18 patients had enrolled into Part B and had been actively followed for at least 3 months or had discontinued from study treatment. If Part C was implemented, 1 interim analysis was planned after 18 patients had been enrolled and had been actively followed for at least 3 months or had discontinued from study treatment. Details of the decision criteria for the planned interim analyses are provided in Section [12.2.14](#).

The 2 planned interim analyses described for Parts A and B in Amendment (b) have been completed (December 2012 and June 2013).

With Amendment (c), the study planned to enroll approximately 190 patients: 109 patients have been enrolled in Part A (37 in Cohort 1, 72 in Cohort 2); 40 are planned for Part B, and 40 for Part C (amended to enroll Child Pugh A patients who had not received any prior systemic therapy and were to be treated with LY2157299 plus sorafenib in a safety lead-in followed by an expansion at the selected dose).

With Amendment (d) and the addition of Part D, an additional 15 patients may be enrolled. With Amendment (e) and the addition of Part E, approximately 23 additional patients may be enrolled.

The primary objective of the study now is to characterize the TTP distributions, the effect on TGF- β -associated serum biomarkers (for example, TGF- β , AFP, E-cadherin) and the relationship between biomarker response and efficacy endpoints of:

- 1) Each of the 2 doses of LY2157299 in second-line patients or patients ineligible to receive sorafenib with HCC who have elevated AFP levels (Part A, Cohorts 1 and 2),
- 2) In second-line patients or patients ineligible to receive sorafenib with HCC who have AFP levels $<1.5x$ ULN dosed at 300 mg/day (Part B),
- 3) In first-line patients with HCC treated with 2 doses of LY2157299 in combination with sorafenib. If the decision in Part C is to use only 1 treatment group in the expansion cohort, the results from patients at the other dose will simply be listed.
- 4) In second-line patients with HCC treated with LY2157299 given for 21 days on followed by 7 days off (Part E).

For efficacy endpoints, no formal hypothesis testing based on a priori power calculations is planned; rather differences in various endpoints (eg, hazard ratios for TTP, OS) between appropriate treatment groups will be estimated. Since Part C patients are different in 2 ways from patients in Parts A and B (first-line versus second-line and treated with LY2157299 in combination with sorafenib compared to LY2157299 monotherapy, respectively), the only estimate of differences between Parts A and/or B with Part C will be between Part C and the sorafenib-naive patients from Parts A and B. The interpretation of any estimate will be considered in light of the size of this subgroup.

Data from patients from Part D and E will be summarized separately from the data in Parts A, B, and C.

12.2. Statistical and Analytical Plans

12.2.1. General Considerations

Statistical analysis of this study will be the responsibility of Eli Lilly and Company.

All patients who receive at least 1 dose of study drug will be evaluated for safety, efficacy, toxicity, and progressive disease endpoints. The progressive disease responses will especially focus on the AFP kinetics and the TGF- β 1 levels but also include the assessments of EMT-associated markers (for example, E-cadherin) and fibrosis-related blood markers.

Patients with measurable disease will be included in summaries of tumor response. Tumor response will only be tabulated for patients who received at least 1 dose of study drug and have measurable disease at baseline.

After Amendment (b), patients are allowed to continue on study treatment at the investigator's discretion, even when objective progression is determined by radiological measurements, if they do not have overall symptomatic deterioration as well. This change should not affect the primary objective (estimation of TTP), PFS, or response rate. However, bias may be introduced in the assessment of OS, since patients prior to Amendment (b) will have discontinued based on objective progression alone. It is therefore important to capture patients enrolled in each amendment.

Patients from all sites will be pooled for the purposes of analysis. All confidence intervals of treatment effects will be provided at a 2-sided alpha level of 0.10, unless otherwise stated. Patients with Child-Pugh Class A and B7 will be considered as 1 group of patients, given the similarity of Class B7 patients to Class A patients. If all patients in Part A and Part B are second-line, Part C patients will be analyzed as a separate group. If there are some first-line patients in Part A or Part B, different subgroups may be required. Part D will be conducted outside of the EU. Data from patients from Parts D and E will be analyzed separately from Parts A, B, C.

Any change to the data-analysis methods described in the protocol will require an amendment ONLY if it changes a principal feature of the protocol. Any other change to the data-analysis methods described in the protocol, and the justification for making the change, will be described in the clinical study report. Additional exploratory analyses of the data will be conducted as deemed appropriate.

12.2.2. Definition of Clinical Efficacy Measures

Anticancer therapy is considered any treatment after failure or discontinuation on LY2157299.

Best response is determined from the sequence of cycle responses assessed. For complete response (CR) or partial response (PR), best response must be confirmed. A second assessment should be performed ≥ 28 days after the first documentation of response. Two objective status determinations of CR before progression are required for a best response of CR. Two determinations of PR or better before progression, but not qualifying for a CR, are required for a best response of PR. Best response of stable disease (SD) is defined as disease that does not meet the criteria for CR, PR, or progressive disease and has been evaluated at least 1 time, at least 6 weeks after start of study treatment.

Evidence of progression is as defined in the RECIST 1.1 criteria (primary method) and mRECIST for both determining clinical response and time-to-event endpoints except for OS.

The following definitions for time-to-event measures will apply:

- OS duration is measured from the date of randomization to the date of death from any cause. For each patient who is not known to have died as of the data-inclusion cut-off date for a particular analysis, OS duration will be censored for that analysis at the date of last prior contact.

- PFS duration is measured from the date of randomization to the first date of progression of disease or of death from any cause. For each patient who is not known to have died or to have had a progression of disease as of the data-inclusion cut-off date for a particular analysis, PFS will be censored at the date of last prior contact. PFS duration will be calculated and analyzed twice: (1) including clinical progressions of disease not based on lesion measurements, and (2) excluding clinical progressions.
- Time to progressive disease is measured from the date of randomization to the first date of progression of disease. For each patient who is not known to have had a progression of disease as of the data-inclusion cut-off date for a particular analysis, or who has died without progression of disease, time to progressive disease will be censored for that analysis at the date of the patient's last tumor assessment prior to that cut-off date. Time to progressive disease will be calculated and analyzed twice: (1) including clinical progressions of disease not based on lesion measurements, and (2) excluding clinical progressions.
- Duration of tumor response is measured from the date of the first objective status assessment of a CR or PR to the first date of progression of disease or death from any cause. For each patient who is not known to have died or to have had a progression of disease as of the data-inclusion cut-off date for a particular analysis, duration of tumor response will be censored at the date of last prior contact.
- Time to treatment failure is measured from the date of randomization until the date of discontinuation of study treatment due to AE, progression of disease, or death from any cause. For each patient who has discontinued study treatment for any other reason, time to treatment failure will be censored at the date of discontinuation of study treatment. If a patient is still on study treatment as of the data-inclusion cut-off date for the particular analysis, time to treatment failure will be censored for that patient at that cut-off date.

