One cycle is defined as 28 days (a minimum of 26 days and a maximum of 31 days). The treatment period for LY2157299 must be a minimum of 10 days and a maximum of 14 days (for Parts A, B, C and D) and 21 days (for Part E); the “off-treatment” period can vary to ensure an overall cycle length of 26 to 31 days). In extenuating circumstances, the “on study drug” window for LY2157299 is allowable from Day 10 to Day 14. (In Part C and D safety lead-in Cycle 1, patients must have received 14 days of LY2157299 treatment). For Part E Cycle 1, all patients must receive 21 days of treatment, followed by 7 days off treatment. If patients are not evaluable for DLT assessment and/or PK in Cycle 1 of Part C or Part D safety lead-in, or Cycle 1 Part E, the patients will be replaced.

Per patient, the screening period is no more than 4 weeks or 28 days before the first dose of LY2157299; the planned treatment duration is 6 cycles or approximately 24 weeks, but patients may continue to receive study drug if they are still benefiting from treatment in the opinion of the investigator and Lilly physician. Follow-up visits will occur approximately 30 days after the last day of study treatment and subsequently approximately every 60 days (approximately 2 months [± 7 days]).

In case of the occurrence of severe toxicities in later cycles in patients treated with either LY2157299 monotherapy or LY2157299 in combination with ramucirumab or sorafenib, the sponsor will review and choose a lower dose or discontinue the patient, if necessary.

The final analysis for Parts A and B will be conducted after the study objectives for these 2 parts have been met. This is likely to be after approximately 30 deaths have occurred in Part B in order to have a reasonable estimate of overall survival in this patient group (AFP <1.5x ULN).

Part C will be considered complete and the final analysis initiated once 85% of events for survival analysis in the expanded cohort in Part C have occurred.

Part D will be considered complete and the final analysis initiated after the last patient has discontinued from study treatment and completed at least the 30-day follow-up visit [Visit 801].

Part E will be considered complete and the final analysis initiated after the last patient has discontinued from study treatment and completed at least the 30-day follow-up visit [Visit 801].

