12.2.8. Clinical Efficacy Analyses

Kaplan-Meier analysis will be performed on the observed distribution of TTP (Kaplan and Meier 1958) for each dose in Part A, Part B, Part C, Part D and Part E, with parameter estimates of the TTP median and quartiles being reported. All parameter estimates will be quoted together with their 90% confidence limits. The hazard ratio between the observed TTP distributions of each cohort in Part A will be estimated, recognizing that since 1 dose cohort did not enroll to its full

complement, the precision of the HR will be lower than originally planned. The hazard ratios between the 300 mg/day cohort in Part A and Part B cohort will also be estimated. In addition, the hazard ratio between a subgroup of sorafenib-naïve patients in Parts A and B and patients in Part C may be estimated. The interpretation of any estimate will be considered in light of the size of this subgroup.

Alternative distributions of TTP times, such as exponential Weibull (estimating a shape parameter may also be considered) where median TTP and its 90% CIs will be reported. Individual parameters, such as TTP rate after specific time points (for example, after 12 months on treatment) will be estimated from the TTP distribution.

Secondary efficacy measures include other time-to-event parameters, and these will follow the same analyses as described above.

The overall response rate (ORR) for each cohort in Part A, Part B, Part C, Part D and Part E will be estimated by dividing the total number of confirmed responders by the number of patients who received at least 1 dose of study treatment. The clinical benefit rate will be estimated for each treatment group by dividing the total number of patients experiencing benefit by the number of patients who received at least 1 dose of study treatment. A patient is considered to have received benefit if they achieve a confirmed response, CR or PR, or SD per RECIST v1.1 or mRECIST. Both mean and exact confidence limits will be provided for each group (Cohort 1 and Cohort 2 in Part A, Part B, Part C, Part D and Part E, as well as estimates of differences between 2 cohorts in Part A, between Parts A and B at 300 mg/day, and between sorafenib-naïve patients in Part A and Part B with those in Part C. The interpretation of any estimate in the latter comparison will be considered in light of the size of this subgroup.

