Attachment 1. Protocol JBAK Study Schedule

Parts A and B

Cycle/Visit ^j	Prestudy			Cycle 1					Cycle 2		Cycle 3, n ^l		Extension Period	Visit 801	Follow-up ^f	Comments
	≤28	≤14	≤7	1 ⁱ	8 ⁱ	14 ⁱ	15	22	1 ⁱ	14 ^{i,k}	1 ⁱ	14 ^{i,k}				
Procedures																
Informed Consent	X															Informed consent must be signed prior to performing any study procedures.
Medical History		X														
Child-Pugh, Barcelona Clinic Liver Cancer (BCLC), and CLIP staging			X ^h													
Pregnancy Test			X													
Physical Exam		X		X		X			X	X	X		X	X		Starting in Cycle 3, to be performed once per cycle. Perform predose on Day 1 of each cycle in extension period.
Vital Signs (heart rate, blood pressure)		X		X		X			X	X	X		X	X		Starting in Cycle 3, to be performed once per cycle. Perform predose on Day 1 of each cycle in extension period.
CTCAE Grading		X		X		X			X	X	X		X	X	X ^a	Starting in Cycle 3, to be performed once per cycle. Perform predose on Day 1 of each cycle in extension period.
Concomitant Medications		X		X					X		X		X	X	X	Perform predose on Day 1 of each cycle in extension period.
Performance Status		X		X		X			X	X	X		X	X		Starting in Cycle 3, to be performed once per cycle. Perform predose on Day 1 of each cycle in extension period.

Cycle/Visitj	Prestudy			Cycle 1					Cycle 2		Cycle 3, n ^l		Extension Period	Visit 801	Follow-up ^f	Comments
	≤28	≤14	≤7	1 ⁱ	8 ⁱ	14 ⁱ	15	22	1 ⁱ	14 ^{i,k}	1 ⁱ	14 ^{i,k}				
Tumor Assessment, Physical (Palpable or Visible)		X		X					X		X			X		Optional during the extension period (including extension period V801)
Imaging Procedures																
Echocardiography with Doppler ^g	X								X		X		X	X ^b	X ^b	Cycle 2, 3, 4, and every other cycle (C6, C8,...etc). Perform predose on Day 1 of each cycle in extension period
Chest CT Scan or Chest MRI		X											X	X ^c		CT scan or MRI every 6 months
Tumor Assessment, Radiological		X								X	X			X ^d	X ^d	Tumor assessment every 6 weeks starting Cycle 2, Day 14. May be performed 3 days around the scheduled date. Optional during the extension period (including extension period V801)
ECG		X							X		X		X	X ^b	X ^b	Cycle 2, 3, 4, and every other cycle (C6, C8,...etc). Perform predose on Day 1 of each cycle in extension period

Cycle/Visit ^j	Prestudy			Cycle 1					Cycle 2		Cycle 3, n ^l		Extension Period	Visit 801	Follow-up ^f	Comments
	≤28	≤14	≤7	1 ⁱ	8 ⁱ	14 ⁱ	15	22	1 ⁱ	14 ⁱ , k	1 ⁱ	14 ⁱ , k				
Laboratory /Diagnostic Tests																

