For efficacy endpoints, no formal hypothesis testing based on a priori power calculations is planned; rather differences in various endpoints (eg, hazard ratios for TTP, OS) between appropriate treatment groups will be estimated. Since Part C patients are different in 2 ways from patients in Parts A and B (first-line versus second-line and treated with LY2157299 in combination with sorafenib compared to LY2157299 monotherapy, respectively), the only estimate of differences between Parts A and/or B with Part C will be between Part C and the sorafenib-naïve patients from Parts A and B. The interpretation of any estimate will be considered in light of the size of this subgroup.

Safety:

Summary statistics, plots, and listings for all safety data collected will be provided in aggregate and by dose in Part A and Part C, and in aggregate for Part B separately. Comparisons between doses and parts will be summarized for Part A and Part B, and may be compared to Part C. Comparisons between other subgroups of interest may be required.

Any change to the data-analysis methods described in the protocol will require an amendment ONLY if it changes a principal feature of the protocol. Any other change to the data-analysis methods described in the protocol, and the justification for making the change, will be described in the clinical study report. Additional exploratory analyses of the data will be conducted as deemed appropriate.

The following data handling conventions will be used in the analysis.

Term	Definitions or Rule
Study day	
If assessment is on or after date of first treatment dose then $(\text{date of assessment}) - (\text{date of first study treatment dose}) + 1$
 
If assessment precedes first treatment dose then $(\text{date of assessment}) - (\text{date of first study treatment dose})$
 
There is no study day 0. Study day 1 is the date of first dose and study day -1 is the day before the first dose.

Cycle day	
If assessment is on or after date of first treatment dose then $(\text{date of assessment}) - (\text{date of first study treatment dose in cycle}) + 1$
 
If assessment precedes first treatment dose then $(\text{date of assessment}) - (\text{date of first study treatment dose in cycle})$
 
There is no cycle day 0. Cycle day 1 is the date of first dose in the cycle and cycle day -1 is the day before the first dose.

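### The protocol's 6-week minimum for stable disease excludes first scans that its own schedule allows, and the SAP gives no minimum, so the two documents can produce different clinical benefit rates

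*Protocol*

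**What the plan says.** **SD rule.** Protocol 12.2.2 allows a best response of SD when disease is not CR, PR or progression and "has been evaluated at least 1 time, at least 6 weeks after start of study treatment". It gives no tolerance.

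**Scan schedule.** Protocol Attachment 1, for Parts A and B: "Tumor assessment every 6 weeks starting Cycle 2, Day 14. May be performed 3 days around the scheduled date". The schedules for Parts C, D and E carry the same comment.

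**Cycle length.** Protocol 7.1: "One cycle is defined as 28 days (a minimum of 26 days and a maximum of 31 days". For Part E it adds: "For Part E Cycle 1, all patients must receive 21 days of treatment, followed by 7 days off treatment".

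**Day count.** SAP 5.3.3: "Study day 1 is the date of first dose and study day -1 is the day before the first dose". Neither document says whether this convention governs the 6-week rule.

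**Endpoint.** Protocol 12.2.8: "A patient is considered to have received benefit if they achieve a confirmed response, CR or PR, or SD per RECIST v1.1 or mRECIST". The numerator is divided "by the number of patients who received at least 1 dose of study treatment".

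**SAP.** Section 5.1.1 lists clinical benefit rate as a secondary efficacy endpoint and includes SD in it. The same section restates the confirmation rules for CR and PR but gives no minimum time for SD.

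**The concern.** The SD minimum and the first scan are both set at about 6 weeks, but only the scan has a window. A site can scan exactly as the protocol permits and still produce an assessment that the protocol will not accept as SD. Two patients with the same disease course, stable at the first scan and progressed at the second, are then classified differently because one was scanned a few days earlier within the allowed window.

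The affected patient leaves the numerator of the clinical benefit rate and remains in the denominator, so under the protocol rule the error runs one way, downward. SAP 5.3.8.1 reports this rate with exact 90% intervals and compares it between cohorts and parts with chi-squared tests and odds ratios. In the small parts a single reclassification is visible: 1/23 is about 4 points in Part E, and 1/18 is about 6 points in Part D.

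A programmer following Protocol 12.2.2 and one following SAP 5.1.1 could report different rates from the same scans.

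**Working it through.** The plan states no figure to reproduce. The check is date arithmetic, followed by a rough gauge of size.

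**Step 1: day of the first scan.** With first dose as study day 1 (SAP 5.3.3):

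study day = length of Cycle 1 + 14 + window shift (−3 to +3); elapsed days = study day − 1.

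| Cycle 1 length | Earliest | Scheduled | Latest |
|---|---|---|---|
| 26 days | 26 + 14 − 3 = 37 | 40 | 43 |
| 28 days | 28 + 14 − 3 = 39 | 42 | 45 |
| 31 days | 31 + 14 − 3 = 42 | 45 | 48 |

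Part E fixes Cycle 1 at 21 + 7 = 28 days, so its earliest compliant day is 39.

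**Step 2: compare with 6 weeks.** Six weeks is 42 days. If study day 42 counts, scans on days 37 to 41 fail. If 42 elapsed days are required (study day 43), day 42 fails too.

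- 28-day Cycle 1: 3 of the 7 window days fail on the first count, 4 of 7 on the second.
- All permitted combinations (6 cycle lengths × 7 window days = 42): 15 of 42 (36%) fail on the first count, 21 of 42 (50%) on the second.

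**Step 3: who is exposed.** The second scan is due at about day 42 + 42 = 84. Any later scan without progression satisfies the rule. The patients at risk are those stable at an early first scan who have progressed by the second, or who have no second scan.

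**Step 4: rough size.** Inputs are the median times to progression in Protocol 5.1.5.2: 11.9 weeks (Part A, 109 patients) and 18.0 weeks (Part B, 40 patients). Assuming an exponential distribution, S(t) = 0.5^(t/median).

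- Part A: S(6) − S(12) = 0.705 − 0.497 = 0.208, about 23 of 109.
- Part B: S(6) − S(12) = 0.794 − 0.630 = 0.164, about 7 of 40.

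Multiply by the share of early first scans, taking all permitted combinations as equally likely (an assumption):

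- Part A: 0.208 × 15/42 = 0.074, and 0.208 × 21/42 = 0.104, so about 7 to 10 points.
- Part B: 0.164 × 15/42 = 0.059, and 0.164 × 21/42 = 0.082, so about 6 to 8 points.

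Real scan dates will not be spread evenly. If all scans fell on the scheduled day of a 28-day cycle, nobody would be lost when day 42 counts, and the whole pool from this step would be exposed when it does not. The schedule describes 6-weekly scans starting at that visit, which suggests that the authors regard it as week 6. On that reading the figures above are on the high side.

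**The case against.** Five points can fairly be made against this.

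1. **The SAP supplied has no 6-week minimum.** Applied as written, it would count SD on day 39 as benefit. This stands. A reader might infer that the reported rate is biased downward outright; the documents support that only if the protocol rule is the one programmed. What is certain is that the documents differ.

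2. **The scheduled day itself may be fine.** A reader might infer that every on-schedule scan is one day short, because study day 42 is 41 elapsed days. That requires applying the SAP's study-day convention to a protocol phrase that fixes no count, so it is not established. The failure on days 37 to 41 does not depend on it.

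3. **Few patients may be reached.** An early first scan alone excludes nobody, and Protocol 10.1 asks for 6-weekly imaging to continue after treatment stops until progression. This limits the route through a missing second scan, but not the route through progression at the second scan.

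4. **The endpoint is minor.** Clinical benefit rate is not named among the secondary objectives in Protocol 6.2, and both documents disclaim formal powered testing of efficacy. Time to progression and overall response rate do not use the rule. All this stands and limits the importance. Nor do the documents show that the effect differs between cohorts.

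5. **Some text cannot be seen.** The RECIST 1.1 attachment is redacted, the mRECIST attachment is not shown, and the SAP supplied aligns with Amendment (c). A timing rule elsewhere cannot be excluded. It would still have to be reconciled with the explicit sentence in 12.2.2.

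**Conclusion.** The concern holds. The SD minimum in Protocol 12.2.2 conflicts with the protocol's own scan window: compliant first scans on study days 37 to 41 (39 to 41 with a 28-day Cycle 1) cannot support SD. Under that rule, patients who are stable then and progress by the next scan, or have no later scan, are counted as having no benefit. The SAP supplied is silent on the minimum, so the two documents can yield different rates.

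The effect is confined to the clinical benefit rate and its SD component. Its size cannot be determined without the actual scan dates. The 7 to 10 points for Part A and 6 to 8 for Part B rest on three assumptions: the protocol rule is applied, time to progression is exponential, and 36% to 50% of first scans are early. They are rough upper figures and should not be quoted as an estimated bias. Progression found at scans moves in steps, and a median cannot show how large the step at the second scan is.

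**What to change.** State one SD rule in Protocol 12.2.2 and SAP 5.1.1, for RECIST 1.1 and mRECIST alike: SD may be based on the first protocol-scheduled scan when it is done within its allowed window, that is on study day 37 or later (26 + 14 − 3 = 37). Say explicitly that first dose is day 1 for this purpose.

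Apply the rule prospectively to the parts not yet analysed, through the next SAP version; Protocol 12.2.8 already plans one before the first Part E dose. Parts A and B are already reported (Protocol 5.1.5.2), so changing their definition now would be post hoc. For them, give the rate under the new rule as a sensitivity analysis, with the number of patients whose classification changes.

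No new data are needed. The cost is a slightly more lenient SD minimum: up to 5 days if day 42 is taken as 6 weeks (42 − 37), or 6 days if 42 elapsed days are required (43 − 37). The sensitivity analysis needs only scan dates already collected.
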